11.1.6.2. Sample Collection, Storage, and Shipping

Clinical laboratory samples will be collected by appropriate clinical site personnel and then shipped according to a separate laboratory manual provided by the central laboratory.

Blood draws for lipids, TG, and glucose must meet the fasting criterion listed below. If this criterion has not been met, these blood samples will NOT be collected. If this criterion can be met by rescheduling the clinic visit to occur within 3 days, the lipid, TG, and/or glucose blood samples will be collected at the rescheduled clinic visit only.

- Blood samples will be drawn after a minimum 10-hour fast (water is allowed)

11.1.6.3. General Monitoring and Management of Abnormal Clinical Labs

It is the investigators' responsibility to review the results of all laboratory tests as they become available and to sign and date the report to document their review. For each laboratory test outside of the laboratory normal range, the investigator needs to ascertain if this is a clinically significant change from baseline for the individual patient, with baseline defined as the last value

or observation before the first dose of study drug. The investigator may repeat the laboratory test or request additional tests to verify the results of the original laboratory test.

If a laboratory value is determined to be an abnormal and clinically significant change from baseline for the patient, the investigator should determine if it qualifies as an AE (as described below), and if yes, an appropriate eCRF will be completed. All clinically significant laboratory abnormalities occurring during the study that were not present at baseline should be followed and evaluated with additional tests if necessary, until diagnosis of the underlying cause or resolution. Specific monitoring and management guidelines for laboratories of special interest are outlined in the sections below.

An abnormal laboratory value that is not already associated with an AE is to be recorded as an AE only if any one of the following criteria is met:

- an action on the study drug is made as a result of the abnormality
- intervention for management of the abnormality is required
- at the discretion of the investigator should the abnormality be deemed clinically significant

11.1.6.3.1. Monitoring and Management of Elevated Liver Function Tests

If at any time after randomization a patient experiences a new ALT and/or AST $>3 \times$ ULN, the patient will undergo repeat confirmatory liver function test (LFT) assessment as soon as is reasonably possible, preferably within 3 to 7 days of the laboratory result becoming available.

Repeat LFT assessment will include: (1) measurement of ALT, AST, alkaline phosphatase, total and direct bilirubin, prothrombin time (PT)/international normalized ratio (INR), eosinophil count, CK, antihepatitis A virus (total), HBsAg (confirmation of screening measurement), hepatitis C virus (HCV) (confirmation of screening measurement), and anti-cytomegalovirus/immunoglobulin M; (2) history of concomitant medication use; (3) history of exposure to environmental chemical agents, including ethanol; and (4) query for related symptoms. Additionally, further testing such as liver ultrasound or magnetic resonance imaging (MRI) scanning may be warranted to rule out additional pathology depending on clinical presentation and should be discussed with the Sponsor personnel or the authorized Medical Monitor.

- If repeat LFT assessment confirms ALT and/or AST $>3 \times$ ULN, consideration should be given to withdrawing the patient and administering no further doses of study drug. At the investigator's discretion, study drug may be interrupted and the patient rechallenged with study drug after LFTs have returned to baseline levels.
- If repeat LFT assessment confirms ALT and/or AST $>5 \times$ ULN, patient should be withdrawn from IMP treatment, but will be asked to continue to be followed for safety using the protocol-specified visit schedule (see [Appendix 1](#)) or more frequently as determined by the investigator.
- If repeat LFT assessment confirms ALT and/or AST $>3 \times$ ULN in addition to any of the following, the patient should be given no further IMP treatment, but will be asked

to continue to be followed for safety using the protocol-specified visit schedule (see [Appendix 1](#)) or more frequently as determined by the investigator:

- TB $>2 \times$ ULN

Note: In the case of patients with Gilbert's disease, TB will be fractionated and the determination of $2 \times$ ULN will be based upon direct (conjugated) bilirubin.

- INR $>1.5 \times$ ULN (unless the patient is on stable dose of anticoagulation medication)
- Appearance or worsening of right upper abdominal discomfort, anorexia, fatigue, nausea, vomiting, fever, rash, or eosinophilia

11.1.6.3.2. Monitoring and Management of Elevated Serum Creatinine

If at any time after randomization, a patient experiences a decrease in eGFR to the level of 15 mL/min/1.73 m²) or if the patient experiences acute renal failure, the patient should be withdrawn from IMP treatment but will be asked to continue to be followed for safety using the protocol-specified visit schedule (see [Appendix 1](#))

11.1.6.3.3. Monitoring and Management of Hemoglobin Change

If at any time after randomization a patient experiences a Hgb decrease >2.0 g/dL (20 g/L) from baseline (Week 0 [Visit T1]), the patient will undergo repeat confirmatory hematology testing as soon as is reasonably possible, preferably within 3 to 7 days of the laboratory result becoming available.

Repeat hematology assessment will include: (1) measurement of Hgb, hematocrit (Hct), mean corpuscular hemoglobin, mean corpuscular hemoglobin concentration, mean corpuscular volume, platelet count, reticulocyte count (percent and absolute), red blood cell count (RBC), and white blood cell count (WBC) with differential (absolute values only); (2) history of concomitant medication use; and (3) query for related symptoms. Additionally, further testing may be warranted to rule out additional pathology depending on clinical presentation, and should be discussed with Sponsor personnel or the authorized Medical Monitor.

- If repeat Hgb assessment confirms a decrease >2.0 g/dL (20 g/L) from baseline, the patient should be monitored carefully during the study and return at 2-week intervals after study completion for additional Hgb measurement until the level returns to baseline or reaches a stable level.
- If repeat Hgb assessment confirms Hgb <8 g/dL (80 g/L), the patient should be withdrawn from IMP treatment. The patient will return at 1-week intervals after withdrawing from IMP treatment for additional Hgb measurement until the level returns to baseline or reaches a satisfactory conclusion.
- If the patient is withdrawn from IMP treatment, the patient should be asked to continue being followed for safety using the protocol-specified visit schedule (see [Appendix 1](#)).

At any time, the investigator may choose to consult with a specialist to further evaluate the cause of the alteration in Hgb.

11.1.6.3.4. Monitoring and Management of Elevated Creatine Kinase

If at any time after randomization a patient experiences a marked CK elevation $>5 \times$ ULN, the patient will undergo repeat confirmatory assessment as soon as is reasonably possible, preferably within 3 to 7 days of the laboratory result becoming available.

Repeat CK assessment will include query for related symptoms.

- If the repeat CK assessment confirms an unexplained (ie, not associated with recent trauma or physically strenuous activity) CK abnormality $>5 \times$ ULN, if asymptomatic the patient should receive further assessment and investigation into the cause, assess whether there is renal injury, and measure CK approximately weekly or more frequently if clinically indicated until resolution. If CK levels continue to rise; IMP and study-supplied ezetimibe should be discontinued.
- If symptomatic, the following steps should be completed:
 - Hold IMP and study-supplied ezetimibe
 - Clarification of the nature, duration, and intensity of muscle symptoms
 - Review possible predisposing factors, such as unaccustomed exercise, heavy alcohol intake, viral illness (consider performing serology)
 - Evaluation for additional diagnoses or other conditions which can cause myopathy including muscle tenderness (by PE), weakness, rash, measurement of serum creatinine, dipstick urinalysis with microscopy if indicated
 - Obtain clinical chemistries to assess the possibility of lactic acidosis
 - Follow symptoms and CK until the abnormality has resolved
 - If based on the above evaluation an alternative explanation is suspected, consideration can be given to resuming IMP once CK returns to baseline levels
 - If no alternative explanation exists, consideration should be given to withdrawing the patient from IMP treatment.
- If the repeat CK assessment confirms an unexplained (ie, not associated with recent trauma or physically strenuous activity) CK abnormality as listed below, the patient should be withdrawn and given no further doses of study drug:
 - $>10 \times$ ULN, even in the absence of symptoms.
 - In all cases, evaluate the signs/symptoms and laboratory evaluations as outlined above.
- If the patient is withdrawn from IMP treatment, the patient should be asked to continue being followed for safety using the protocol-specified visit schedule (see [Appendix 1](#)).

11.1.6.3.5. Monitoring and Management of Potential Hypoglycemia and Metabolic Acidosis

Patients will be educated on the signs and symptoms of hypoglycemia. If such signs and symptoms are experienced, patients will be instructed to report these signs and symptoms to the investigator.

During each study visit, patients will be reminded to report all signs and symptoms associated with hypoglycemia to the investigator. For each occurrence of patient-reported signs and symptoms associated with hypoglycemia, the investigator will discuss these symptoms with the patient and assess whether they are attributable to hypoglycemia or to another potential cause. All investigator-confirmed occurrences of hypoglycemia will be recorded as an AE. All occurrences of signs and symptoms that are not confirmed by the investigator to be attributable to hypoglycemia will be reported using the appropriate diagnosis.

Clinical laboratories will be assessed to determine any signs of anion gap metabolic acidosis. If laboratories are consistent with metabolic acidosis, immediate follow up with the patient for further medical evaluation of the acidosis. This event should be captured as an AE.

11.1.6.3.6. Monitoring and Management of Elevated Triglycerides

Patients may continue to use stable doses of TG-lowering medications during the study. An adjunctive therapy plan is in place for those patients whose TG values meet the protocol-defined threshold criteria. Post-randomization, TG results will be masked to investigators in order to maintain the blind; however, a threshold has been set to notify investigators and provide an opportunity to adjust the patient's standard of care regimen. Beginning at Week 4 (Visit T2), if the TG level exceeds 1000 mg/dL (11.3 mmol/L) while on treatment, the investigator will receive notification from the central laboratory that the patient has met or exceeded the protocol-defined threshold criteria for TG. The investigator will initiate the following plan:

- Any patient with TG >1000 mg/dL (11.3 mmol/L), will be reminded to fast for at least 10 hours and will return to clinic within 1 week for a repeat, fasting TG sample to confirm the TG value meets the threshold criteria
- Any patient with a confirmed TG >1000 mg/dL (11.3 mmol/L) may initiate standard-of-care therapy to lower TG using a patient-specific prescription. The initiation of this medication will be documented on the case report form as a concomitant medication with the associated start date. These medications will not be provided by the Sponsor.
- Patients continuing to exceed the TG threshold after maximizing the standard-of-care triglyceride-lowering therapy will be discontinued from IMP treatment and will be asked to continue to be followed for safety using the protocol-specified visit schedule (see [Appendix 1](#)).
- Please see the Clinical Laboratory Manual and [Section 11.1.6.2](#) for sample collection and instructions.

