Limited vendors (ie, the bioanalytical laboratory and other vendor personnel, if any, that are responsible for PK analysis) will have access to the randomization codes to facilitate PK analytical work, and will be instructed to not communicate in any manner information associated with treatment assignment to any personnel at the clinical site, the Sponsor, or contract research organization (CRO).

Post-randomization values for individual laboratory measures for LDL-C, TG, TC, HDL-C, non-HDL, apoB, and hs-CRP that may inadvertently suggest treatment assignment will not be available to personnel from the clinical site, the patient, the Sponsor, or CRO.

A blinded independent expert Clinical Events Committee (CEC) will adjudicate designated clinical endpoints, including all major adverse cardiac events (MACE) and non-MACE endpoints defined as: CV death (MACE), non-CV death (non-MACE), nonfatal myocardial infarction [MI] (MACE), nonfatal stroke (MACE), hospitalization for unstable angina (MACE), coronary revascularization (MACE), non-coronary arterial revascularization (non-MACE), and hospitalization for heart failure (non-MACE) using standardized definitions. Any clinical endpoints that meet SAE criteria will be reported as SAEs.

An independent expert Data Monitoring Committee (DMC) will formally review accumulating unblinded safety data from this and other ongoing studies of bempedoic acid.

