10.3. Subject Withdrawal Criteria

10.3.1. Early Withdrawal from the Study

Patients must remain in the study until the last scheduled visit at Week 12 (Visit T4) to be considered as having completed participation in the study.

Patients who withdraw from IMP and/or ezetimibe prior to Week 12 (Visit T4) for any reason will be asked to continue to be followed for safety assessments, including basic fasting lipids, at clinic visit following the protocol-specified visit schedule (see [Appendix 1](#)).

Patients who temporarily withdraw from IMP and/or ezetimibe prior to Week 12 (Visit T4) for any reason may restart IMP and/or ezetimibe providing that (1) the patient and the investigator are in agreement regarding this course of action, (2) the patient has been off of IMP for 4 weeks or less; and (3) IMP can be started as soon as possible. For cases where the patient has been off of IMP for more than 4 weeks, the investigator must contact the medical monitor for approval prior to restarting IMP.

Patients who refuse to continue to return to the clinic for safety assessments will be asked to participate in phone calls from the site at protocol-specified visits (see [Appendix 1](#)), or at a minimum at 12 weeks, to collect information on AEs, concomitant medications, and current health status.

The patient's decision to participate in the clinical study is voluntary. Patients may refuse to continue in the study and/or withdraw from participation in this study at any time, for any reason, specified or unspecified, and without penalty or loss of benefits to which the patient is otherwise entitled.

It is the right and duty of the investigator to interrupt the treatment of any patient whose health or well-being may be threatened by continuation in this study. Such patients should be withdrawn from the study and should not be continued under a modified regimen.

Patients who are withdrawn from the study may not re-enter. The reasons for withdrawal from this study may include:

- Patient's withdrawal of consent
- Failure to comply with the protocol
- Lost to follow-up
- Illness, condition, or procedural complication (including AEs) affecting the patient's ability to participate or requiring prohibited medication
- The Sponsor or investigator terminates the study
- In the investigator's judgment, it is deemed in the best interest of the patient to discontinue his/her participation in the study
- Any other reason

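### Triglycerides are masked on every sample after randomization, but the >1000 mg/dL laboratory notice is worded to cover only patients on treatment, so samples taken off IMP have no stated alert

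*Protocol*

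**What the plan says.** Section 11.1.6.3.6 sets the mask: "Post-randomization, TG results will be masked to investigators in order to maintain the blind". Section 8.6 repeats it more broadly: "Post-randomization values for individual laboratory measures for LDL-C, TG, TC, HDL-C, non-HDL, apoB, and hs-CRP that may inadvertently suggest treatment assignment will not be available". It withholds those values from site personnel, the patient, the Sponsor and the CRO. Neither section limits the mask to samples drawn while the patient takes IMP.

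Section 11.1.6.3.6 then offers a threshold notice as the counterpart of the mask. From Week 4 (Visit T2), "if the TG level exceeds 1000 mg/dL (11.3 mmol/L) while on treatment, the investigator will receive notification from the central laboratory". A fasting repeat within a week, optional TG-lowering therapy and, if TG stays above the threshold, discontinuation of IMP follow from that notice.

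Section 10.3.1 provides for sampling off IMP. Patients who stop IMP and/or ezetimibe "will be asked to continue to be followed for safety assessments, including basic fasting lipids" on the normal visit schedule. Appendix 1, footnote 9, counts triglycerides among the basic fasting lipids. The same section lets patients interrupt and restart IMP if, among other conditions, "the patient has been off of IMP for 4 weeks or less". A longer interruption needs the medical monitor's approval before restart.

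**The concern.** The mask and the notice do not cover the same samples. The mask applies to everything after randomization, while the notice carries a treatment condition. For a scheduled TG sample taken after IMP is stopped or held, the investigator cannot see the value and, as the sentence reads, is not promised the message that stands in for it.

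What is at stake is patient safety rather than inference. The protocol treats a TG above 1000 mg/dL as calling for prompt confirmation and possible therapy, and that need does not end when IMP stops. Section 11.1.6.3.6 itself creates such patients: those whose TG stays above the threshold on maximized therapy are taken off IMP and kept on the visit schedule. The general duty in Section 11.1.6.3 to review laboratory results does not help, because it covers results as they become available, and masked TG results do not become available.

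**Working it through.** The finding rests on comparing sections. The plan gives no figure to reproduce.

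**Step 1: coverage of each rule.**

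| Rule | Section | Samples covered |
|---|---|---|
| TG masked | 8.6, 11.1.6.3.6 | all after randomization |
| Fasting lipids continue after IMP stops | 10.3.1, Appendix 1 | T2, T3, T4, on or off IMP |
| Notice at TG >1000 mg/dL | 11.1.6.3.6 | from T2, with an on-treatment condition |

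On the plain wording, what is masked but not covered by the notice is every TG sample from T2 onward taken off IMP. No other section gives a TG alert or unmasks TG after IMP stops.

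**Step 2: comparison with the neighbouring triggers.** The liver rule begins "If at any time after randomization a patient experiences a new ALT and/or AST", the renal rule "If at any time after randomization, a patient experiences a decrease in eGFR" and the hemoglobin rule "If at any time after randomization a patient experiences a Hgb decrease". The creatine kinase rule in Section 11.1.6.3.4 has the same scope. None of those four values is masked, and none of the four triggers has a treatment condition. TG is the masked parameter and the only one of the five with such a condition.

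**Step 3: meaning of the condition.** If it meant the 12-week treatment period, it would be redundant. The sentence already starts at Week 4, and every scheduled visit from then on (T2, T3, T4) lies in that period. Section 12.5 uses a similar expression for drug status when it chooses the imputation strategy by whether a patient is still on study treatment.

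**Step 4: size.** From the protocol: 225 patients, with scheduled TG samples at Days 29, 57 and 85. Assumed, because the protocol gives no rates: 5-15% stop IMP permanently, at times uniform over Days 1-85, and all are followed; 0.1-1% of their later samples exceed 1000 mg/dL (entry excludes TG of 500 mg/dL or more).

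- Samples remaining after a stop: 3 if before Week 4, 2 if between Weeks 4 and 8, 1 if after Week 8. The three intervals are 28 days each, so the mean is (3 + 2 + 1)/3 = 2.0.
- Patients off IMP: 225 × 0.05 = 11.25 to 225 × 0.15 = 33.75.
- Off-IMP samples: 11.25 × 2 = 22.5 to 33.75 × 2 = 67.5, out of 225 × 3 = 675, or 3.3% to 10.0%.
- Alerts missed: 22.5 × 0.001 = 0.02 to 67.5 × 0.01 = 0.68.

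A patient stopped for refractory TG has at most 1 or 2 samples left. The first alert can come only at T2, and a repeat sample and maximized therapy must come before the stop. Temporary holds are not in this count.

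**The case against.** The strongest reply is that the condition is loose drafting for the double-blind treatment period. The protocol usually says IMP treatment when it means the drug, including later in Section 11.1.6.3.6, whereas this phrase is unqualified. Visits from T2 on are headed as treatment weeks. The sentence that introduces the threshold and the first two action bullets carry no treatment condition. The wording is imprecise elsewhere too: the trigger requires TG to exceed the threshold, while the message says the patient has met or exceeded it. A patient off IMP may also still be taking study ezetimibe.

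A second reply is practical. The central laboratory issues the notice, and the protocol nowhere describes it being told IMP status; discontinuation goes to the eCRF and IWRS (Section 10.3.2). The alert may therefore fire regardless. The Clinical Laboratory Manual, which is not at hand, could say so, although Section 11.1.6.3.6 cites it only for sample collection and instructions.

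Third, there are backstops: local testing, visits at any time for safety, DMC review of unblinded data, and the investigator's existing knowledge of patients stopped for refractory TG.

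Part of this stands. The phrase is ambiguous, the restrictive reading is firmer for a permanent stop than for a brief hold, and whether an alert would actually be lost cannot be settled from the protocol. But the benign reading leaves the words with no function, and a laboratory could programme its alert to the narrower one. None of the backstops is a prompt notice on a value the investigator cannot see. If the wider reading was intended, the sentence still needs correcting.

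**Conclusion.** The concern holds, as a minor defect in safety wording. TG is masked for all post-randomization samples, and the only stated exception, read plainly, leaves out samples taken off IMP that the protocol itself schedules. The expected effect is below one missed alert in the trial (about 0.02 to 0.7). That range depends on the assumed rates of stopping IMP and of extreme TG, on full follow-up and evenly spread stop times, and on the narrower reading of the phrase. In patients stopped for refractory TG the investigator already knows of the problem, so only the automatic notice on their later study samples is lost. The primary and secondary analyses, power and type I error are unaffected.

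**What to change.** In Section 11.1.6.3.6, delete the three-word on-treatment condition from the trigger sentence, or replace it with a statement that the notice applies to every post-randomization TG sample from Week 4 regardless of IMP status. Confirm that the central laboratory's alert specification matches. The management steps can stay as they are. The cost is a change of three words and one check with the laboratory. No extra samples are needed, and because the notice works the same way in both arms, extending it adds no new kind of unblinding.
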